Our Engagement Panel is adapted from a previously developed model of patient engagement,^{49, 50} and is comprised of 12 Veterans who have lived-experience with PTSD, including 6 men and 6 women of diverse race and ethnicity, 25-67 years old. The panel meets quarterly and more often, as requested to support ongoing projects. Meetings of 2-3 hours are organized by the CCDOR Engagement Workgroup, with input from project teams on topics and goals. Meetings begin with a brief investigator presentation on overall project goals and 2-3 key questions for panel members to address. Workgroup staff facilitate meetings, take detailed notes during meetings and review themes with project teams immediately afterwards. Investigators are also provided written summaries of key feedback. Co-Investigator [name] will lead collaboration with the Veteran Engagement Panel on session formats and topics (eg, additional barriers to address), communication materials (eg, brochures and worksheets for activity planning), and recruitment procedures.

3. Adaptation of GET and integration with motivational interviewing

We will combine GET and motivational interviewing in individual meetings and group sessions to be delivered by a trained PT.

At the first individual meeting, participants will complete in-person baseline assessments, learn about intervention rationale and components, discuss their values and goals, describe preferences for types of physical activity (eg, walking), and be introduced to mHealth components. Weekly group sessions in month 1 will involve closed cohorts of 6-8 participants and be conducted by video-conferencing (see Section 4b below). Based on our experience with motivational interviewing, chronic pain rehabilitation, and PTSD psychotherapies, the group format should optimize development of relationships and support between participants, while also permitting personalized attention to motivations and barriers. Additionally, groups may be particularly beneficial for individuals with PTSD, who are often isolated and have greater difficulty making

The proposed 4-month intervention will focus on initiation (months 1-2) and maintenance (months 3-4) of higher physical activity levels (Figure 2). In month 1, sessions will employ GET and motivational interviewing to provide intensive, personalized counseling, thereby over-coming barriers to initiation. In month 2, further gains in physical activity will be supported by

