We propose to conduct a pilot study of 3 groups with 6-8 participants each (total n=18-24). Based on our clinical and research experience with piloting group interventions, and number of participants in the active arm of recent pilot studies of group exercise interventions for PTSD,^{25, 26} we expect that 3 groups will provide sufficient data on feasibility and acceptability to inform a larger study. A control group will not be enrolled as examining efficacy is not appropriate at this stage,^{53, 54} and our main goal is to evaluate feasibility and acceptability of the active intervention. Co-Investigator [name] will be the PT interventionist conducting in-person assessments, video-conferencing sessions, and telephone calls. We will use a concurrent mixed-methods approach to assess feasibility and acceptability, and anticipate making protocol modifications as appropriate. Data on physical activity, functioning, and symptoms will also be collected, to determine feasibility of outcomes assessments for a future randomized trial.

1. Human Subjects Involvement & Characteristics.

We will screen Veterans being seen in-person or having virtual care appointments at MVAHCS primary care clinics for PTSD (ie, ≥3 on Primary Care Screen for PTSD-5) and self-reported health-related limitations in mobility (ie, climbing several flights of stairs or walking several blocks). Exclusion criteria include ongoing suicidal ideation or psychosis; medical contraindications to exercise (eg, complete paraplegia); high degree of disability (ie, impairments in ≥2 basic activities of daily living); plans to move out of the area permanently within 4 months; major neurocognitive impairment (eg, dementia), schizophrenia; acute mental health crisis within the past 3 months (requiring an ED visit or hospitalization); and routinely completing 150 minutes or more of moderate to vigorous activity per week. We will not recruit prisoners, institutionalized individuals, or children. Our goal is to conduct 3 groups of 6-8 participants each (18-24 total).

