Inclusion: 1) ≥ 18 years old; 2) patient in primary care at MVAHCS; 3) score ≥ 3 on Primary Care PTSD Screen (PC-PTSD-5), which is routinely administered during primary care appointments (95% sensitivity and 85% specificity for PTSD diagnosis⁵⁵); 4) “yes” to any of 3 questions about health-related limitations from the Veterans RAND 36-Item Health Survey (VR-36),^{56, 57} as an indicator of impaired functioning; 5) has access to device (smart phone, tablet, or computer) that enables participation in videoconferencing; 6) has a smartphone or tablet that can support Garmin application; 7) has internet access for videoconferencing.

Exclusion: 1) active suicidal ideation or psychosis; 2) medical contraindication to participation (eg, complete paraplegia); 3) self-reported impairments in 2 or more activities of daily living (ADLs); 4) plans to move out of area permanently within next 4 months; 5) major neurocognitive impairment (e.g., dementia); 6) schizophrenia; 7) acute mental health crisis within the past 3 months (requiring an ED visit or hospitalization); and 8) routinely completing 150 minutes or more of moderate to vigorous activity per week. Individuals meeting these criteria may be unable to safely increase physical activity at home or not have a need for this program.

For Veterans referred by primary care and PCMHI staff, the study coordinator and/or principal investigator will conduct further eligibility screening using the following sources: 1) review of medical records for exclusion criteria (recent episodes of psychosis and medical contraindications to physical activity); 2) discussion with primary care provider for clarification about potential contraindications, as needed; and 3) telephone call to administer questions on mobility limitations, other health problems, and ADL impairments. For Veterans who self-refer, the study coordinator will first complete the PC-PTSD-5 and screening questions for suicidal ideation. After completing screening for eligibility, the study coordinator will schedule Veterans for a phone call to obtain informed consent and provide additional information on the intervention.

4. Informed Consent Procedures

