The study coordinator will schedule a telephone call with Veterans to go over the informed consent form, HIPAA authorization form, and enrollment forms for financial incentives. We will also include other materials to describe the study (eg, FAQ document, expectations for confidentiality and privacy during group meetings, and troubleshooting Zoom). We will mail potential participants these materials ahead of the phone call, instructing them not to sign any forms until the call. During the call, the study coordinator will provide a thorough overview of study participation, risks, benefits, alternatives, protections, and IRB and study staff contact information. We will emphasize the voluntary nature of study participation and provide the opportunity for questions about the study. The consent process will be conducted by the study coordinator, who is trained in the ethics of human subject research. Those who agree to participate will mail back signed informed consent and HIPAA authorization forms via prepaid stamped envelopes. Signed informed consent and HIPAA authorization forms will be received by the study team before collection of any participant data.

5. Quantitative Data & Analyses (Table 4)

Feasibility will be quantitatively assessed as **recruitment** (proportion enrolled out of total identified as eligible), **attendance** (proportion who attend $\geq 75\%$ of in-person visits), and **retention** (proportion who complete post-intervention assessments). To determine feasibility, we will first evaluate recruitment and time needed to enroll participants. We anticipate approximately

20 Veterans per month may be eligible (based on preliminary data noted above), and with 20% recruitment, we expect to complete enrollment for each group in 4-6 weeks. We have set attendance and retention benchmarks at 75%, which are realistic estimates based on recent pilot studies of group exercise interventions for PTSD (participants attended an average of 78-82% of sessions and overall retention were 76-82%).^{25, 26}

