5-8	
Individual Sessions #4-7 (Virtual via Phone, 10-15 min, weekly)
 
 • Troubleshooting home activity plan • Gradually increase activity goals • MI: Self-efficacy, amplify change talk, roll with resistance
16	
Final In-Person Assessment (60 min)
 
 • Post-intervention Assessments: 
 ○ Physical functioning (VR-36,^{56,57} 6-minute walk,^{58,59} and 30-second sit to stand^{59,60}) ○ Other study measures* • Disconnect Garmin Vivosmart 4 device from I CARE Study account

*PTSD symptoms (PTSD Checklist for DSM-5 [PCL-5]^{61,62}); depressive symptoms (Patient Health Questionnaire-8 [PHQ-8]⁶³); pain (brief 3-item scale on intensity and interference [PEG]⁶⁴); fatigue (PROMIS 4-item fatigue short form⁶⁵); sleep quality (PROMIS sleep disturbance and impairment)^{66, 67}; self-efficacy (PROMIS general 4-item⁶⁸ and one item specific to physical activity); and social support for physical activity (1 item).

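### The 4-month move-away exclusion has no stated start date and, counted from screening, ends before the week-16 in-person visit for Veterans screened early in a cohort's fill period

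*Combined protocol and SAP*

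**What the plan says.** The criterion appears twice in the combined protocol and SAP. Exclusion 4 in section 5.0 C.3 reads "plans to move out of area permanently within next 4 months"; section 5.0 C.1 has "plans to move out of the area permanently within 4 months". Neither gives a start date.

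Eligibility is settled before consent. Section C.3 states: "After completing screening for eligibility, the study coordinator will schedule Veterans for a phone call to obtain informed consent". Under C.4 the consent forms are mailed out, discussed by telephone and mailed back. No later check of moving plans is described.

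The cohorts are closed. Section B.3 says: "Weekly group sessions in month 1 will involve closed cohorts of 6-8 participants". On filling them, section C.5 assumes that "20 Veterans per month may be eligible" and that 20% will be recruited, and concludes "we expect to complete enrollment for each group in 4-6 weeks".

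The Appendix 2 schedule starts with an in-person baseline visit at week 0. Its week-16 entry begins "Final In-Person Assessment (60 min" and includes the walk and sit-to-stand tests. C.5 defines retention as the proportion completing the post-intervention assessments, with a benchmark of 75%.

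**The concern.** The 4-month window matches the nominal length of the intervention and makes almost no allowance for the wait between screening and the start of a closed group. A Veteran screened early in the fill period, who says a permanent move is planned for, say, four and a half months ahead, passes the criterion as written. The final visit may fall after that move.

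Such a loss would be known in advance and would say nothing about whether the intervention is feasible, yet it would count as a retention failure. It would also enter the C.6 matrix that compares themes between participants who did and did not complete the post-intervention assessments. There is an oddity as well: someone with a move planned at month 5 passes at screening but would meet the same criterion if asked again a little over a month later, which may be before the cohort starts.

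**Working it through.** **Inputs.** Window: 4 months (C.1, C.3). Final visit: week 16 (Appendix 2). Group size: 6-8 (B.3). Stated fill time: 4-6 weeks (C.5). Accrual: 20 eligible per month, 20% recruited (C.5). Total sample: 18-24. Conversion: 365.25 / 12 / 7 = 4.348 weeks per month.

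**Step 1: the plan's own fill time.** Accrual is 20 × 0.20 = 4 per month.
- Group of 6: 6 / 4 = 1.5 months = 6.5 weeks.
- Group of 8: 8 / 4 = 2.0 months = 8.7 weeks.

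The stated 4-6 weeks is not reproduced. Four-week months give 6-8 weeks. Counting only the gaps between first and last enrollee gives 5 / 4 and 7 / 4 months, or 5.4-7.6 weeks. Filling 6-8 places in 4-6 weeks would need about 22% recruitment (6 people in 6 weeks) to 43% (8 people in 4 weeks). Both bases are therefore carried forward, separately.

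**Step 2: slack in the window.** 4 × 4.348 = 17.4 weeks, and 17.4 − 16 = 1.4 weeks.

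**Step 3: screening to final visit.** Time = wait for cohort start + 16 weeks, assuming that week 0 falls when the group is full.

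| Enrollee | Wait (weeks) | Total (weeks) | Months |
|---|---|---|---|
| Last in the group | about 0 | 16 | 3.7 |
| First, stated fill, low | 4 | 20 | 4.6 |
| First, stated fill, high | 6 | 22 | 5.1 |
| First, implied fill, group of 6 | 6.5 | 22.5 | 5.2 |
| First, implied fill, group of 8 | 8.7 | 24.7 | 5.7 |

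For the first enrollee the uncovered period is 0.6-1.1 months on the stated fill time and 1.2-1.7 months on the implied one. Time for mailed consent is not quantified in the documents and would lengthen every row.

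**Step 4: share of a cohort with a final visit beyond the window.** If screening is spread evenly over the fill period (an assumption), the share is 1 − 1.39 / fill time.
- Stated fill: 65% at 4 weeks, 77% at 6 weeks.
- Implied fill: 79% at 6.5 weeks, 84% at 8.7 weeks.

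Mean time to the final visit is (fill time / 2 + 16) / 4.348: 4.1-4.4 months (stated) or 4.4-4.7 months (implied). These are shares of participants whose visit date lies outside the window, not shares who plan to move.

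**Step 5: weight of one loss.** 1 / 24 = 4.2 points; 1 / 18 = 5.6 points. Meeting 75% needs 14 of 18 (0.75 × 18 = 13.5, rounded up) or 18 of 24, so 4 or 6 losses can be absorbed. One relocation uses a quarter or a sixth of that allowance.

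**The case against.** The strongest reply is that the start date is inferred. If the 4 months ran from the baseline visit or cohort start, 16 weeks (3.7 months) would fit and there would be no gap. That is fair, and it limits the point to an undefined window that falls short on its natural reading. It does not remove the point, because the criterion is applied at screening and nothing in the plan re-asks it later.

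The purpose is also inferred. The only rationale C.3 gives for the exclusions is safety at home and lack of need for the program; it does not mention protecting the final visit. Nor does a move make attendance impossible, since a person could return for one visit, and a planned move might come up on the consent call. So the Veteran may be lost, not must be.

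A reader might infer that everyone waits 4.6-5.7 months. The documents do not support this. Those figures belong to the first enrollee in a group, and the upper end requires replacing the stated fill time with the recomputed one. Late enrollees are inside the window.

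Finally, 4.2-5.6 points is the cost of losing any one participant for any reason. It is not an estimate of how often this will happen.

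**Conclusion.** The point holds as a low-value, inexpensive improvement. Counted from screening, the exclusion leaves 1.4 weeks beyond the schedule, against a stated fill time of 4-6 weeks. Early enrollees are exposed for up to 0.6-1.1 months on the protocol's own figure, and up to 1.7 months on the recomputed one. It rests on three assumptions: the window starts at screening, moving plans are not re-asked, and the cohort starts when full.

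It would be tempting to conclude that the 75% retention benchmark is in jeopardy. The documents give no rate of planned moves, and a person is affected only if screened early and already planning a permanent move within a short gap. Few are likely to be. What can be said is that any such loss is foreseeable, unrelated to feasibility, and not negligible at this sample size.

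**What to change.** In sections C.1 and C.3, restate exclusion 4 so that it covers Veterans who *plan to relocate permanently before the scheduled week-16 in-person visit of the cohort they would join*. This settles the start-date question and works however long a cohort takes to fill. The coordinator needs an expected visit date for each cohort at screening; if that date slips, the question can be asked again at the baseline visit.

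A longer fixed window from screening is a poorer choice: one wide enough for the first enrollee (up to 5.7 months) would be about two months too wide for the last (3.7 months), excluding people who could finish.

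The cost is one phrase in two places and a very small number of otherwise eligible Veterans excluded. The 4-6 week fill time in C.5 should separately be reconciled with 20 per month at 20%.

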Methods. To increase physical activity for Veterans with PTSD, this project will combine GET, motivational interviewing, and mobile health technology (mHealth) to address attitudinal and behavioral barriers particularly relevant for this group. First, we will work collaboratively with our Veteran Engagement Panel to adapt GET protocols effective for non-PTSD populations (eg, adults with chronic pain or fatigue), and incorporate motivational interviewing and mHealth. We will then pilot test the intervention in 3 consecutive groups of 6-8 participants (total n=18-24) and use concurrent mixed-methods to examine feasibility and acceptability. Quantitative measures will include recruitment (proportion enrolled out of total eligible); attendance (proportion who attend 75% of in-person visits); and retention (proportion who complete data collection post-intervention). Qualitative assessments will involve semi-structured interviews on acceptability of

intervention components (eg, session formats and topics, usability of mHealth), and barriers and facilitators to attendance. At baseline, during and post-intervention, we will also assess overall and physical functioning using Veterans RAND 36-item, 6-minute walk, and 30-second sit to stand, and collect additional data (PTSD symptoms, depression, pain, fatigue, and sleep quality) to inform a future randomized trial.

List of Abbreviations

CCDOR.....	Center for Care Delivery & Outcomes Research
CBT	Cognitive Behavioral Therapy
Co-I.....	Co-Investigator
ED.....	Emergency Department
GET	Graded Exercise Therapy
HSRD	Health Services Research and Development
IRB.....	Institutional Review Board
mHealth	Mobile Health Technology
MVAHCS	Minneapolis VA Health Care System
NIH	National Institutes of Health
PACT	Patient Aligned Care Team (VA primary care staff)
PCMHI	Primary Care Mental Health Integration
PCL-5	PTSD symptom checklist for the DSM-5
PC-PTSD-5.....	Primary Care Screen for PTSD for DSM-5
PEG	Brief 3-item Scale on Pain Intensity & Interference
PHQ-9.....	Patient Health Questionnaire-9
PI	Principal Investigator
PSQI	Pittsburgh Sleep Quality Index
PTSD	Posttraumatic Stress Disorder
PT.....	Physical Therapist
RR&D	Rehabilitation Research and Development
UMN	University of Minnesota
VA.....	Department of Veterans Affairs
VHA	Veterans Health Administration
VINCI.....	VA Informatics and Computing Infrastructure
VR-36	Veterans RAND 36-item Health Questionnaire
WRAP.....	Wearables Research and Analytics Platform

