at regular intervals during the intervention. Participants will also be instructed to contact study staff if any change in health status occurs in between scheduled study follow-ups. The investigative team includes general internal medicine physicians, in addition to the PT interventionist, who will help assess the full range of concerns regarding any changes in participant health status. If an injury is thought to be potentially related to the study, we will follow appropriate MVAHCS IRB policy for reporting and care of participants.

Accuracy and Integrity of Data—Secure Data Infrastructure: VINCI is an HSR&D Resource Center that provides researchers a national view of VA patient data. VINCI is a research and development partnership and operational platform for health services research, epidemiology, decision support, and business intelligence. Partners include VA Office of Informatics and Analysis, and Office of Information and Technology (OIT) Business Intelligence Service Line. VINCI brings together data sources and the analytical environment for performing studies, along with the expertise of data stewards such as VHA National Data Systems (NDS) and VA Information Resource Center (VIReC). New research projects are granted access to dynamic views or data snapshots that can be updated as needed. In addition to data storage, VINCI includes a cluster of servers with dedicated software for analysis, data processing, and extracting information from text. VINCI is accessible from the VA intranet, providing VA researchers with a central, secure location to access data and the applications they need to select, transform, and analyze patient data.

CCDOR also maintains several of its own secure virtual data servers that are protected behind the VA firewall. All individuals with administrative access privileges to the CCDOR servers have been screened and assigned a security clearance to work with patient level data. OIT Administrative access to the data is strictly limited to backing up server data, which prevents catastrophic loss of data. Backups of these servers occur regularly and are stored in a secure location.

2. Recruitment Procedures

Data collection and recruitment will take place at MVAHCS. We will rely primarily on 2 methods of identifying potentially eligible Veterans: 1) primary care staff referral and 2) self-referral.

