Staff Referral: Referrals from primary care staff, including Primary Care Mental Health Integration (PCMHI), will provide our first-line recruitment source, as this will closely model how the patients would receive referrals in typical clinic care. We will make announcements about the study in multiple settings and forums (eg, announcements at team meetings, presentations at grand rounds). We will provide flyers and brochures to staff and discuss the study with them. We will ask primary care staff to provide potentially eligible Veterans (ie, positive on PTSD screen and without suicidal ideation, see detailed inclusion and exclusion criteria below) with brochures about the pilot study. If a Veteran demonstrates interest, primary care staff will either encourage Veteran to directly call study coordinator (information in brochure) or ask for permission to share their name and telephone number with the coordinator.

Self-Referral: To facilitate self-referral, we will use study fliers and brochures strategically placed in appropriate clinic locations and make announcements to inform primary care staff about the study. Individuals who are self-referred to the study will reach out to study staff to express their interest directly.

Active Outreach: Due to decreased in-person visits during the COVID pandemic (which limit opportunities for staff and self-referrals), we will identify potentially eligible Veterans who have a positive screen for PTSD in the past 2 months through an administrative data pull and recruit these Veterans through mailed letters and telephone calls. We will send out letters introducing the study and providing contact information for individuals to opt out of further contacts. Starting 10 days after the letter is sent, we will make up to 3 calls (on at least 2

different days) to provide more information about the study and conduct eligibility screening, for those who are interested.

3. Inclusion/Exclusion Criteria

To identify Veterans with PTSD symptoms and poor physical functioning who may benefit from the intervention, eligibility criteria are as follows (**Error! Reference source not found.**):

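### Is the recruitment rate uninterpretable because the plan does not say at which stage a Veteran enters its denominator?

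*Combined protocol and SAP*

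**What the plan says.** Recruitment is one of three quantitative feasibility measures, beside attendance and retention. Section 5.0 C.5 gives it as the "proportion enrolled out of total identified as eligible". The Methods paragraph of the opening summary gives it as the "proportion enrolled out of total eligible". C.5 also plans to look at the time needed to enrol. It forecasts about 20 possibly eligible Veterans a month, 20% recruitment and 4-6 weeks to fill each group. Attendance and retention have a 75% benchmark; recruitment has none.

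Section 5.0 C.2 describes three routes into the study, and on each the Veteran shows interest before study staff screen:

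- Staff referral: "If a Veteran demonstrates interest, primary care staff will either encourage Veteran to directly call study coordinator", or agree to have their contact details passed on.
- Self-referral: "Individuals who are self-referred to the study will reach out to study staff to express their interest directly".
- Active Outreach: letters, then up to three calls, in which staff "conduct eligibility screening, for those who are interested".

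Section 5.0 C.3 lists seven inclusion and eight exclusion criteria. Mobility limits and impairments in daily living are asked about by telephone. The consent call is scheduled once screening is complete.

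**The concern.** The two definitions differ by two words, and neither fixes the stage of counting. Other places in the plan can be read as pointing to a wider group. Section 5.0 C.2 uses the language of identification for people not yet screened: "We will rely primarily on 2 methods of identifying potentially eligible Veterans", and for outreach "we will identify potentially eligible Veterans who have a positive screen for PTSD in the past 2 months through an administrative data pull". Section 5.0 C.1 says "We will screen Veterans being seen in-person or having virtual care appointments at MVAHCS primary care clinics for PTSD", with no mention of interest. The forecast in C.5 starts from Veterans who might qualify, which also sounds like a pool counted before contact.

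The candidates give different rates. If only interested and screened Veterans are counted, then eligible Veterans who opt out, are not reached or decline before screening are left out, and the rate is higher than uptake. If the whole data-pull list is counted, the outreach denominator includes ineligible people, and the rate is lower than uptake. The pilot exists to inform a randomised trial, and a team that took a conversion rate for uptake would plan to approach too few Veterans.

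**Working it through.** **1. The plan's own forecast.** Inputs from Section 5.0 C.5: 20 Veterans a month, 20% recruitment, 4-6 weeks per group. Group size is 6-8 and the total 18-24 (Section 3.0, Aim 2).

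- Enrolled per month = 20 × 0.20 = 4.
- Months per group = 6/4 to 8/4 = 1.5 to 2.0.
- Weeks per group, at 52/12 weeks a month = 6.5 to 8.7; at 4 weeks a month = 6 to 8.

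The stated 4-6 weeks is not reproduced, except for six participants in six weeks with a four-week month. That is a separate arithmetic matter. It does not show which denominator is meant, and nothing below relies on it.

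**2. What the denominator is worth in numbers.**

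- Eligible Veterans implied by 20% = 18/0.20 to 24/0.20 = 90 to 120, which takes 90/20 to 120/20 = 4.5 to 6 months.
- Let i be the share of eligible Veterans who reach screening. The documents give no value, so those below are assumptions.
- If 20% is conversion, the eligible pool is 90/i to 120/i. At i = 0.8 this is 112.5 to 150; at i = 0.5 it is 180 to 240.
- If 20% is uptake, conversion is 0.20/i. At i = 0.8 this is 25%; at i = 0.5 it is 40%.
- At i = 1 the two readings agree.

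The possible gap is large, but it is set entirely by i. The plan's figures cannot narrow it.

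**3. Which reading the text supports.**

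| Reading | In favour | Against |
|---|---|---|
| Screened and found eligible | C.3 lists the criteria and places screening directly before the consent call; C.2 puts interest before screening on all three routes | The stage is not written into the definition |
| Data-pull list | C.2 uses the verb identify for this list | C.2 calls these Veterans *potentially* eligible, and the definition in C.5 drops that qualifier; a positive PTSD screen meets one of seven inclusion criteria |
| All eligible Veterans in clinic | Summary wording; C.1; the forecast in C.5 | The study cannot count eligible Veterans it never screens; C.1 is a general description and the forecast is not the definition |

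Eligibility rests partly on what the Veteran reports: health-related limits, access to a device and internet, and impairments in daily living. Someone who opts out or is never reached cannot be confirmed as eligible, so the first reading is the one that can be computed on all three routes.

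**4. Whether a fuller set of outreach rates would recover uptake.** The idea is that enrolled/letters sent and enrolled/screened-eligible lie either side of uptake. This holds for enrolments credited to outreach, because screened-eligible ≤ eligible ≤ letters sent. It need not hold for all eligible letter recipients. In an assumed example, 100 letters go out and 50 recipients are eligible. Staff referral reaches 10 of these first and all 10 enrol. Outreach screens 20 as eligible and enrols 4.

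- Outreach rates: 4/100 = 4% and 4/20 = 20%.
- Uptake among eligible recipients: (10 + 4)/50 = 28%, above both.

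The extra reporting would describe one route. It would not deliver the missing uptake figure.

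**The case for a change.** The strongest opposing case is that a rate with no benchmark has value only through its interpretation, and interpretation needs a stated denominator. Recruitment is the measure C.5 says is evaluated first, and a later trial would plan from it. Time to enrol would reveal slow accrual but not whether poor reach or poor conversion caused it. Pooling self-referred Veterans with people contacted cold also gives a mixture that another trial may not share. Contact outcomes not tallied at the time may be hard to rebuild, and the plan does not commit to reporting them.

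Part of this stands. The stage is not stated, and the rate must not be read as uptake. The forecast's loose wording is the best support for a wider reading. The basis of the 20% cannot be checked either: C.5 refers to preliminary data that are not in the text supplied, and since pages were removed this cannot be held against the plan.

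The rest does not amount to a fault. The feared error needs a later team to treat the rate as something the plan never calls it, with the recruitment steps set out in C.2 and C.3. The difference from the summary reads as compression: the same paragraph shortens the attendance criterion, giving 75% where C.5 has at least 75%. Counts by route and by contact outcome are good reporting practice, but neither the definition nor any planned conclusion depends on them.

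**Conclusion.** The concern does not hold as a defect. It is a gap in wording that analysts would fill sensibly, because the criteria and the order of steps lead them to count Veterans screened and found eligible. Followed that way, the plan yields a valid conversion rate. With no recruitment benchmark, no pass or fail result could change.

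The 90-120 eligible Veterans implied by 20% follows from the plan's figures. The wider pools of about 113-150 and 180-240 rest only on assumed values of i (0.8 and 0.5) and are not evidence of an error of that size. The conclusion assumes that eligible in C.5 means meeting the criteria in C.3, and that the results are described as conversion. If they were presented as uptake among all eligible Veterans, that claim would be unsupported, but the plan does not make it.

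### The 4-6 weeks allowed to enrol each group does not follow from 20 eligible Veterans per month at 20% recruitment, which gives about 6-9 weeks

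*Combined protocol and SAP*

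**What the plan says.** All the accrual inputs are in Section 5.0 C.5 (Quantitative Data & Analyses). Recruitment is the "proportion enrolled out of total identified as eligible". The expected flow is approximate: "20 Veterans per month may be eligible (based on preliminary data noted above". From these the plan concludes that "with 20% recruitment, we expect to complete enrollment for each group in 4-6 weeks".

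The group size is the same throughout. Section 5.0 C states "We propose to conduct a pilot study of 3 groups with 6-8 participants each (total n=18-24", and Section 5.0 B.3 states "Weekly group sessions in month 1 will involve closed cohorts of 6-8 participants". Because the cohorts are closed, a group has to be filled before its sessions begin.

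Section 5.0 C.5 also gives enrolment time a role in judging feasibility: "To determine feasibility, we will first evaluate recruitment and time needed to enroll participants". Numerical benchmarks (75%) are set only for attendance and retention.

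**The concern.** The stated time looks too short for the stated flow and uptake. One fifth of 20 per month is 4 people per month, so a group of 6-8 needs one and a half to two months, not 4-6 weeks.

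What is at stake is how the pilot's accrual will be read. The 4-6 weeks is the only expectation given for enrolment time. If flow and uptake turn out exactly as assumed, groups of 7 or 8 would be expected to overrun it and a group of 6 would at best just meet it. Accrual that is fully on plan could then be reported as slower than planned, and a future trial could be scheduled on an enrolment time that the inputs do not support.

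**Working it through.** **Inputs**
- Eligible Veterans: about 20 per month (Section 5.0 C.5).
- Recruitment: 20%, with eligible Veterans as the denominator (Section 5.0 C.5), so it multiplies the 20 directly.
- Group size: 6-8, closed cohorts, three groups, 18-24 in total (Sections 5.0 B.3 and 5.0 C).
- Weeks per month: not stated. Both 4 and 52/12 = 4.33 were tried.

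**Enrolment rate:** 20 x 0.20 = 4 per month, which is 1.0 per week (4-week month) or 4/4.33 = 0.923 per week (calendar month).

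**Trying to reproduce the stated 4-6 weeks**

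Weeks = group size / 4 x weeks per month.

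| Group size | 4-week month | Calendar month |
|---|---|---|
| 6 | 6.0 weeks | 6.5 weeks |
| 7 | 7.0 weeks | 7.6 weeks |
| 8 | 8.0 weeks | 8.7 weeks |

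The stated range is not reproduced under either convention. In the other direction, 4-6 weeks yields 4.0-6.0 enrolled (4-week month) or 3.7-5.5 (calendar month), against the 6-8 needed.

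**Size of the gap, matching ends of the ranges**
- 4-week month: 6/4 = 1.50 and 8/6 = 1.33, so 33-50% longer than stated.
- Calendar month: 6.5/4 = 1.63 and 8.67/6 = 1.44, so 44-63% longer.

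**What 4-6 weeks would require**, taken as 6 people in 4 weeks and 8 people in 6 weeks (4-week month / calendar month)

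| Requirement | 6 in 4 weeks | 8 in 6 weeks |
|---|---|---|
| Eligible per month at 20% uptake | 30.0 / 32.5 | 26.7 / 28.9 |
| Uptake at 20 eligible per month | 30.0% / 32.5% | 26.7% / 28.9% |
| Eligible Veterans already identified at opening | 10 / 11.5 | 10 / 12.3 |

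The last row is the total eligible needed minus the new flow in the window. Totals needed are 6/0.20 = 30 and 8/0.20 = 40. New flow is 20 / 18.5 in 4 weeks and 30 / 27.7 in 6 weeks.

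The most favourable pairing, 6 people in 6 weeks, needs only 20.0 / 21.7 eligible per month.

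**Whole pilot:** 18/4 = 4.5 months and 24/4 = 6 months of recruitment.

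**The case against.** The strongest reply is that enrolment need not start from zero. Under Active Outreach (Section 5.0 C.2) the team will "identify potentially eligible Veterans who have a positive screen for PTSD in the past 2 months through an administrative data pull". If that pull held two months of the stated flow (an assumption: 40 eligible), 20% would be 8 people, a full group. The stock actually needed is smaller, about 10-12. This is a possible route, but Section 5.0 C.5 does not use it: the time is derived from a monthly flow and applied to each group. Section 5.0 C.2 gives no yield for the pull, does not say that it is repeated for each group, calls these Veterans only potentially eligible, and starts the calls 10 days after the letter.

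Second, the 20 per month is approximate and comes from preliminary data that are not in the text available here. It may not cover every recruitment source. That limits the finding to whether the stated figures agree with one another, which does not depend on whether 20 is correct. The approximate wording covers the near edge (21.7 against about 20) but not the 27-33 that the full range needs.

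Third, chance variation matters. With Poisson accrual at 4 per month (an assumption), a group of 6 is filled by week 6 with probability 55% (4-week month) or 48% (calendar month), so for the smallest group the upper limit is about an even bet. For 7 or 8 the probability is 20-39%. This stands as a qualification: the miss is likely for the larger groups, not for every group.

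Fourth, little depends on the figure, and that also stands. Even if enrolment and the 16-week programme ran strictly in turn (the plan does not say so), three cycles at 6.5-8.7 weeks would take 3 x 22.5/4.33 = 15.6 to 3 x 24.7/4.33 = 17.1 months. That is inside the 18 months in Section 5.0 A, though beyond the five quarters marked in Table 1. The upper end of the stated range also exceeds those five quarters: 3 x 22/4.33 = 15.2 months.

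**Conclusion.** The stated enrolment time is wrong as written. The plan's own inputs give 6-8 weeks per group (4-week month) or 6.5-8.7 weeks (calendar month), which is 33-63% longer than the 4-6 weeks claimed. Agreement occurs only for 6 people in exactly 6 weeks with a 4-week month.

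This rests on the stated flow and uptake, a steady accrual and no starting stock. It says nothing about whether 20 per month or 20% is realistic. Severity is minor: the sample size, the benchmarks and the direct measurement of uptake are unaffected. The correction is worth making because enrolment time is itself something the pilot sets out to assess.

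**What to change.** Change the sentence in Section 5.0 C.5 in one of two ways.

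1. Restate the expectation as about 6-9 weeks per group, at about 4 enrolled per month, with about 4.5-6 months of recruitment in total for 18-24 participants.
2. Keep 4-6 weeks and state the condition that makes it consistent: about 27-33 eligible Veterans per month at 20% uptake, about 27-33% uptake at 20 per month, or about 10-12 eligible Veterans already identified when each group opens. If the stock is to come from the two-month data pull, give its expected yield and say that it is repeated for each group.

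The cost is one sentence. Under the first option the stated time becomes slightly less favourable; neither option changes the design, the sample size or the procedures, except that repeating the data pull for each group would have to be planned if it is not already.
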